# Multiple Evaluations Within the Same Analysis Window

After all the observations have been slotted based on the table above, if there are multiple valid observations for an assessment within an assigned analysis visit window, only 1 of these observations will be used for summary statistics and analyses. The observation to be used is determined using the following hierarchy (in decreasing order):

- The observation closest to the target study day.
- The later observation if 2 observations are equally close to the target study day.

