- b If the subject has not previously undergone a 6MWT at the study site on the course intended for use during the study, a practice test must be conducted at the Screening Visit and must precede the baseline 6MWT by at least 1 day. To assist with subject scheduling, the baseline 6MWT may be conducted within 24 hours prior to PK sampling (eg, previous day). If the baseline 6MWT is conducted the day prior to PK sampling, then the Week 3 6MWT must also be conducted on the day prior to PK sampling for consistency. If the 6MWT is conducted concurrently with the PK sampling, it should occur between 45 to 60 minutes after the most recent dose. If the Baseline 6MWT is conducted concurrently with PK sampling, then the Week 3 6MWT must also be conducted concurrently with PK sampling. All 6MWTs should be conducted between 10 to 60 minutes after the most recent dose. Prior to the start of each 6MWT, the subject should rest (seated) for at least 10 minutes.
- c The visit window for the Week 3 Visit and the End of Study Visit is ±3 days.
- d The visit window for the Optional Extension Phase Visits is ±5 days. If the subject consents to the Optional Extension Phase of the study, the study will continue with clinic visits every 8 weeks until the study is terminated for any reason or the drug/device becomes commercially available. Additional unscheduled visits may be scheduled as required, for example, to address AEs or to titrate doses as appropriate.
- e Vital signs must be collected after 5 minutes of rest (seated); no other measurements or procedures should be performed during this 5-minute period. When possible, vital signs should be collected prior to the 6MWT. If vital signs cannot be obtained prior to the 6MWT, then they should be obtained after recovery from the 6MWT.
- f For subjects consenting to the optional biomarker sample. For subjects continuing in the Optional Extension Phase, this sample is only required at Week 51 (or upon early termination if prior to Week 51).
- g For subjects consenting to the optional whole genome sequencing sample.
- h For women of childbearing potential.

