3.3.2.3 Vital Signs

Vital signs will be assessed at study visits as specified in Table 3-1. Vital signs measured will include blood pressure (systolic and diastolic), HR, respiratory rate (RR), and weight. Vital signs must be assessed following at least 5 minutes of rest (sitting) to ensure accurate measurement. No other measurements or procedures should be performed during this 5-minute period. When possible, vital signs should be collected prior to the 6MWT. If vital signs cannot be obtained prior to the 6MWT, then they should be obtained after recovery from the 6MWT. Vital signs should also be assessed and reported in the case of abnormal clinical signs and symptoms.

3.3.2.4 12-Lead Electrocardiogram

A 12-lead ECG will be recorded after at least 5 minutes of rest at the Baseline Visit and End of Study Visit or Early Termination Visit. Recordings should include lead II as a rhythm strip and contain at least 5 QRS complexes. ECG parameters to be collected include rhythm, HR, PR interval, QT interval, QRS duration (uncorrected), and any clinically significant abnormalities.

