#### 9.6 ASSESSMENT WINDOWS

For any data summarized by scheduled visit, an analysis visit window will be used. In the protocol, the visit window for the Week 3 Visit and the End of Study Visit is  $\pm 3$  days. The visit window for the Optional Extension Phase Visits is  $\pm 5$  days. In order to allow slotting of discontinuation visits and visits outside the planned schedule, the visit windows have been expanded for analysis purposes. The scheduled visits, as recorded on the eCRFs, and the corresponding target days and study day intervals are specified in Table 9-2. The analysis visit will be derived based on the information specified in Table 9-2.

**Table 9-2** Assessment Windows for Scheduled Visits

Visit	Target Study Day	Study Day Interval	
ECGs			
Baseline	1 Study Day ≤1 (prior to the date of the first dose)		
End of Study Visit		Last assessment after Study Day 1	
	PC	Q-ITD	
Baseline	1	Study Day ≤1 (prior to the date of the first dose)	
Week 3	22	1< Study Day ≤ Last assessment day during Treatment Phase	
End of Study Visit		Last assessment after Study Day 1	
	PAH-S	YMPACT	
Baseline	1	Study Day ≤1 (prior to date of the first dose)	
Week 3	22	1< Study Day ≤ Last assessment day during Treatment Phase	
Week 11	78	Any assessment during Optional Extension Phase	
End of Study Visit		Last assessment after Study Day 1	
Clini	cal laboratory asses	ssments, vital signs, 6MWT	
Baseline	1	Study Day ≤1 (prior to date of the first dose)	
Week 3	22	1< Study Day ≤ Last assessment day during Treatment Phase	
Week 11	78	Last assessment day during Treatment Phase < Study Day ≤106	
Subsequent weeks (every 8 weeks after Week 11)	Week*7+1	Target Study Day-28 < Study Day ≤ Target Study Day+28 or last assessment day during the Optional Extension Phase for final visit	
End of Study Visit		Last assessment in the study	

Abbreviations: 6MWT, 6-Minute Walk Test; ECG, electrocardiogram; PAH-SYMPACT, Pulmonary Arterial Hypertension-Symptoms and Impact; PQ-ITD, Preference Questionnaire for Inhaled Treprostinil Devices; \*, times. Note: Study Day = (Assessment Date) – (First Dosing Date) +1

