#### 12.3 CLINICAL LABORATORY ASSESSMENTS

# 12.3.1 Clinical Chemistry and Hematology

Blood for the measurement and evaluation of clinical chemistry and hematology collected at study visits will be used to assess treatment-emergent changes in clinical chemistry and hematological laboratory parameters. Values will be obtained for the parameters listed in Table 12-1.

**Table 12-1** Clinical Laboratory Parameters

Electrolyte Panel Chemistry Panel		Hematology Panel
Bicarbonate	Alanine aminotransferase	Hemoglobin
Chloride	Aspartate aminotransferase	Hematocrit
Potassium	Bilirubin (total and indirect)	Red blood cell count
Sodium	Creatinine	White blood cell count
	Blood urea nitrogen	Platelet count

Values that are "high" or "low" with respect to the reference range provided by the central laboratory will be flagged with an "H" or an "L," respectively. All parameters will be listed for all subjects and assessments, along with their respective "high/low" flags.

Values of these parameters at each visit, and their corresponding changes from Baseline, will be descriptively summarized by TreT dose and overall.

For each parameter, the frequency and percentage of subjects within each TreT dose and overall who had "low," "normal," or "high" Baseline values, then subsequently had "low," "normal," or "high" follow-up values at each visit will be presented in a shift summary.

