# 12.5 ELECTROCARDIOGRAMS

All ECG assessments will be listed for all subjects. This listing will include the HR, the ECG interval from the beginning of the QRS complex to the end of the T wave (QT interval), the QT interval corrected for HR (QTc) (calculated using formulas by both Bazett and Fridericia as described in Section 9.5.2), the time between the P wave and the beginning of the QRS complex in ECG (PR interval), the electrocardiographic wave (QRS) duration, ECG results (normal/abnormal), whether there were clinically significant changes from the Screening Visit, whether abnormalities were present, and details and comments on any abnormalities. The ECG results at Baseline and changes for each post-Baseline assessment will be descriptively summarized by TreT dose and overall at each visit during the Treatment Phase and Optional Extension Phase. In addition, for QTc intervals calculated using both the Bazett and Fridericia methods, the number and percent of subjects with values ≥500 msec and the number and percent of subjects with changes from Screening of <30 msec, 30 to <60 msec, and ≥60 msec will be presented. Additionally, each abnormality will be summarized by the number and percentage of subjects reporting at each visit by TreT dose and overall at each visit during the Treatment Phase and Optional Extension Phase.

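### SAP 9.6 keeps most off-schedule laboratory and vital-sign readings out of the by-visit safety tables, and no worst-value summary brings them back

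*SAP*

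**What the plan says.** The protocol foresees readings between scheduled visits. Section 3.3.2.3: "Vital signs should also be assessed and reported in the case of abnormal clinical signs and symptoms". Table 3-1, footnote d: "Additional unscheduled visits may be scheduled as required, for example, to address AEs or to titrate doses as appropriate". Section 9.2 adds that further laboratory tests may be needed to investigate an adverse event.

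SAP 9.6 sets the scope of windowing: "For any data summarized by scheduled visit, an analysis visit window will be used". It widens the protocol's visit windows so that off-schedule and discontinuation visits can be assigned to a visit. Where several readings share a window, "only 1 of these observations will be used for summary statistics and analyses". The order of choice is "The observation closest to the target study day", then "The later observation if 2 observations are equally close to the target study day".

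The summaries that use these data are by visit:
- Laboratory values and changes are described at each visit, and "follow-up values at each visit will be presented in a shift summary" (SAP 12.3.1).
- Vital signs are described at each visit (SAP 12.4).
- SAP 15.1 lists clinical chemistry, hematology, their shift tables and vital signs (14.3.2.1 to 14.3.3.1). None is titled as a worst-value or any-time table.

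ECGs are set up differently. Table 9-2 has a Baseline row and a single post-baseline row, which takes the final ECG after Day 1 and has no target day. SAP 12.5 asks for "the number and percent of subjects with values ≥500 msec" and for categories of QTc change.

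**The concern.** Safety and tolerability is the primary objective. Vital signs taken because a subject is unwell, and laboratory tests repeated to follow an event, are the readings most likely to be extreme. SAP 9.6 chooses between readings by date alone. A routine value near the target day displaces an abnormal one from weeks earlier, and the minima, maxima and shift counts then describe the routine value.

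This matters most in the Optional Extension Phase. Visits are eight weeks apart, and the protocol encourages upward titration, which may take place at unscheduled visits. Abnormal values between visits could be collected and listed yet enter no laboratory or vital-sign summary.

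**Working it through.** The plan states no figure for this, so the check applies Table 9-2 and the selection order day by day.

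**Inputs**
- Target day = Week × 7 + 1 (Table 9-2): Week 3 = 22, Week 11 = 78, Week 19 = 134. The table itself prints 22 and 78.
- Week 3 window: Day 2 to the last Treatment Phase assessment day, taken as the Week 3 visit.
- Week 11 window: from the next day to Day 106. With Week 3 on Day 22 this is Days 23 to 106, or 84 days.
- Later windows: above target − 28, up to target + 28. For Week 19 this is Days 107 to 162, or 56 days. Since 78 + 28 = 106 = 134 − 28, there is no gap between windows.
- Scheduled visit within ±3 days (Week 3) or ±5 days (extension) of target, from Table 3-1, footnotes c and d.

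**Rule.** Let T be the target, s the scheduled day and d the day of one unscheduled reading. The unscheduled reading is chosen if |d − T| < |s − T|, or if the two distances are equal and d is later than s. Otherwise it loses. The visit day itself is counted as not lost, because a later same-day reading would win the tie.

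**Days not lost, with k = |s − T|**
- Visit on target: 1 (the visit day).
- Visit k days late: (2k − 1) nearer days + the visit day = 2k.
- Visit k days early: (2k − 1) nearer days + the later tie day + the visit day = 2k + 1. In the Week 3 window this falls to 1, because the window closes on the visit day.

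| Window | Visit day | Days in window | Not lost | Lost |
|---|---|---|---|---|
| Week 3 | 19 | 18 | 1 | 17/18 = 94% |
| Week 3 | 22 | 21 | 1 | 20/21 = 95% |
| Week 3 | 25 | 24 | 6 | 18/24 = 75% |
| Week 11 | 73 | 84 | 11 | 73/84 = 87% |
| Week 11 | 78 | 84 | 1 | 83/84 = 99% |
| Week 11 | 83 | 84 | 10 | 74/84 = 88% |
| Week 19 | 129 | 56 | 11 | 45/56 = 80% |
| Week 19 | 134 | 56 | 1 | 55/56 = 98% |
| Week 19 | 139 | 56 | 10 | 46/56 = 82% |

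The other permitted visit days fall between these limits. A Week 3 visit lies at most 3 days from Day 22, so a reading on Days 2 to 18, at least 4 days away, always loses.

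Table 3-1 of the protocol puts Week 3 on Day 21, not 22. With the visit on Days 18 to 24 the Week 3 range is narrower: 19/23 = 83% (visit on Day 24) to 20/21 = 95% (visit on Day 22), with 16/17 = 94% for Day 18.

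**ECGs.** No day count applies. The post-baseline row has no target day, so distance to target cannot decide anything. An interim ECG gives way only because the row takes the final one. SAP 9.6 governs data summarized by visit, and the 500 msec count in SAP 12.5 is not tied to a visit.

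**The case against.** A one-value rule for by-visit tables is coherent and usual, and this is an uncontrolled, descriptive Phase 1b study. Nothing disappears from the report: SAP 9 lists and flags redundant readings, which can be read through for 45 planned subjects. New or worsened symptoms are adverse events under Protocol 9.1.1, and clinically significant laboratory values are reported as adverse events under 3.3.2.5. Some off-schedule readings are also selected. They are used if no scheduled reading exists in the window, which will happen because SAP 1.2.1 records missed extension visits. They are used if nearer the target, if later in a tie, or, through the End of Study row, if last in the study.

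All of this stands, and it limits the point. It does not close the gap. Listings give no counts or extremes, and laboratory values reach the adverse event tables only after a judgement of clinical significance.

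Three stronger readings are tempting and are not supported:
- **That the nearest-to-target rule removes QTc values.** The post-baseline ECG row has no target day, the instruction to measure when symptoms occur covers vital signs and not ECGs, and SAP 12.5 does not confine its counts to a visit.
- **That 75% to 99% of unscheduled readings are lost.** The figures count calendar days. The documents give neither the rate nor the timing of such readings.
- **That the later-of-ties rule makes a reading after the first TreT dose the Baseline.** Table 9-2 restricts Baseline to before the date of the first dose, and the fallback in SAP 9.5.1 is also a pre-dose value. What remains is a wording conflict: a study day of 1 or less includes the first-dose date, while the qualifier excludes it.

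**Conclusion.** The point holds for laboratory data and vital signs. Where a window contains a scheduled reading, most off-schedule readings enter no by-visit or shift summary, and no planned table recovers them. On a day-count basis the scheduled reading prevails on 75% to 95% of days in the Week 3 window, 87% to 99% in the Week 11 window and 80% to 98% in later ones.

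This assumes that the scheduled visit falls inside its protocol window, that the Week 3 visit is the last Treatment Phase assessment (Day 22 for the Week 11 count), and that there is one unscheduled reading, on a different day. How far the tables would understate extremes cannot be computed from the documents.

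For ECGs the finding is only an ambiguity: SAP 12.5 should say whether its QTc counts are per visit or any-time. This is a worthwhile, low-cost improvement to tables that serve the primary objective. It does not show that safety signals would be hidden from the report.

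**What to change.** - **SAP 9.6:** limit the nearest-to-target rule to by-visit descriptive statistics.
- **SAP 12.3 and 12.4:** add on-TreT rows that use every scheduled and unscheduled reading after the first TreT dose, and state where the on-TreT period ends. Give shift from Baseline to worst-low and to worst-high for laboratory parameters, and lowest and highest values for vital signs. Potassium, heart rate and blood pressure can be abnormal in either direction, so one worst row would not serve.
- **SAP 12.5:** state that the 500 msec and QTc-change counts use all post-baseline ECGs.
- **Table 9-2:** reconcile the two halves of the Baseline definition.

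The cost is a few sentences and some extra table rows, with no new data. The drawback is that subjects with more unscheduled readings have more chances of an extreme value. Showing the number of readings per subject beside the worst-value rows would make that visible.

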#### 10 STUDY POPULATION

Unless otherwise specified, all analyses will be performed on the Safety Population as defined in Section 8.

#### 10.1 PATIENT ACCOUNTABILITY

All subjects' disposition information will be listed by individual subject number, including premature study discontinuation status during the Treatment Phase and the Optional Extension Phase, primary reason for premature study discontinuation, number of days on TreT, and enrollment in the Optional Extension Phase.

The listing of subject accountability will include the dates of informed consent, the date of first TreT dose and the date of last TreT dose, and Tyvaso dose at entry. The number of subjects who received TreT, who completed the Treatment Phase, who completed the Optional Extension Phase, and reasons for study discontinuation will be summarized by TreT dose and overall.

#### 10.2 ELIGIBILITY CRITERIA

The status of the entry criteria will be listed for all subjects. The listing will include the date of the initial screening assessment, whether all eligibility criteria were met (Yes/No), and a list of any specific entry criteria not met. The total number of entry criteria violations and the number of violations for each criterion will be summarized by TreT dose and overall.

Additional protocol deviations may be documented throughout the study. All deviations will be reviewed by the clinical team prior to database lock and those that might affect subject safety, pharmacokinetic, or efficacy outcomes will be considered "Major." All other deviations will be classified as "Minor." Protocol deviations will be listed, including the date of the deviation, the type of deviation, the severity of the deviation (Major/Minor), and a description of the deviation. The number of protocol deviations and the number of protocol deviations by type will also be summarized.

#### 10.3 OTHER DESCRIPTIONS OF STUDY POPULATION

# 10.3.1 Demographics

All demographic data will be listed for all subjects, including assessment date, date of birth, age, sex, ethnicity, race, weight, height, and body mass index (BMI). Age, age category (<65 years of age and ≥65 years of age), sex, ethnicity, race, height, weight, and BMI will be summarized by TreT dose and overall. To assess possible changes in the patient population, an additional summary will be created for demographics by time of enrollment: pre- or post-pandemic.

# **10.3.2** Medical History and PAH History

All significant past or ongoing medical conditions will be listed for all subjects. The listing will include the Medical Dictionary for Regulatory Activities (MedDRA) system organ class (SOC) and preferred term (PT) for each condition listed, and whether the condition is ongoing at study entry. These medical conditions will be summarized by PT within each SOC by TreT dose and overall.

The listing of PAH history will include date of PAH diagnosis, time since PAH diagnosis, current PAH diagnosis, and WHO FC. The current PAH diagnosis, time since PAH diagnosis, and WHO FC will be summarized by TreT dose and overall. To assess possible changes in the patient population, an additional summary will be created for PAH history by time of enrollment: pre- or post-pandemic.

# 10.3.3 Concomitant and Background Medications

All concomitant medications recorded on the eCRF will be mapped to a standard name and Anatomical Therapeutic Chemical (ATC) Levels 1 to 4 using the WHODrug Global. The ATC Levels 2 and 4 and verbatim term of all concomitant medications will be listed for all subjects. This listing will include the date started (or indication that drug was ongoing at randomization), date discontinued (or indication that drug was ongoing at end of study), and the condition(s) treated/indication(s). A summary of concomitant medications present at Baseline, a summary of concomitant medications added during the Treatment Phase, and a summary of concomitant medications added during the Optional Extension Phase will include the frequency and percentage of subjects in each TreT dose group and overall. If ATC Level

4 is not available for a medication, ATC Level 3 will be substituted. If ATC Level 3 is not available, ATC Level 2 will be substituted. If ATC Level 2 is not available, ATC Level 1 will be substituted.

The listing of PAH background medications will include the generic term, date initiated, current total daily dose, and date current dose initiated. The number of subjects receiving each PAH background medication and the current total daily dose will be summarized by TreT dose and overall. A similar listing and summary table will also be created for Tyvaso. Additionally, the number and percentage of subjects receiving ERA only, PDE5-I only, and ERA + PDE5-I will be calculated by TreT dose and overall.

#### 11 EFFICACY ANALYSES

#### 11.1 6-MINUTE WALK TEST

All 6MWT data will be listed for all subjects. For each scheduled assessment, this listing will include the date the test was performed (or date the test was intended to be performed if subject is unable to attempt the test), start time of the test, nominal time point, last TreT or Tyvaso dose, hours from last TreT or Tyvaso dose to 6MWT start, if walk was attempted, total distance walked (in meters), and any circumstances that adversely affected the walk (if any) including reason for not attempting test (if any).

Summaries of 6MWT and corresponding changes from Baseline will be provided by TreT dose and overall at each visit during the Treatment Phase and Optional Extension Phase.

Change in 6MWD will be assessed by a paired t-test at each week for the overall group.

Additionally, a line graph presenting the change from Baseline at each week of the Treatment Phase and Optional Extension Phase will be produced.

# 11.2 PREFERENCE QUESTIONNAIRE FOR INHALED TREPROSTINIL DEVICES

Responses to the PQ-ITD will be listed for all subjects. The listing will include the date of the questionnaire, nominal study visit, and all responses for each subject.

Summaries for each question in the PQ-ITD will be provided by TreT dose and overall at Baseline, Week 3, and End of Study Visit. Additionally, figures presenting overall

satisfaction with the inhaler at Baseline, Week 3, and End of Study visit will be produced. For each question that is assessed at both the Baseline and Week 3 visits, the Mantel-Haenszel mean score statistic will be computed to determine if the distribution of assessments for each device is the same. The pseudo SAS code for this analysis is as follows:

```
proc freq;
  tables usubjid*avisit*assessment / cmh;
run;
```

where usubjid is the subject identifier, avisit is the visit identifier (Baseline and Week 3), assessment is the response (Strongly Disagree, Disagree, Neutral, Agree, Strongly Agree), and cmh specifies the Cochran-Mantel-Haenszel statistics.

